TRANSCRANIAL ROTATING PERMANENT MAGNET STIMULATION – STROKE

Study Protocol

This is a two-year randomized double-blind placebo-controlled pilot clinical trial in 30 chronic ischemic stroke patients to assess the safety and efficacy of bilateral multifocal TRPMS treatment. Patients recruited from the stroke clinic at the Houston Methodist Hospital Eddy Scurlock Stroke Center will be randomly assigned in a 1:1 ratio to either the treatment cohort (group 1, 15 patients) or the placebo cohort (group 2, 15 patients). Group 1 and 2 patients will receive active TRPMS treatment and sham treatment (placebo control), respectively. Both patients and investigators evaluating study outcomes will be blinded to treatment assignment. Randomization and coding of patients will be carried out by a research associate who will be involved in constructing, testing, and maintaining the stimulators but will not be participating in any of the evaluation procedures or analysis of data. The research associate will use a list of random numbers generated by a hardware real random number generator for randomization. The research associate will maintain blinding until all data are analyzed by providing real or sham stimulators constructed by the research associate without disclosing their nature to other personnel. Informed consent will be obtained from the patients. They will be compensated for parking. The study will be conducted by the PI [name] with assistance from a study coordinator and a clinical assistant. The sub-investigator [name] will provide technical advice regarding the magnetic stimulator device, guide the operation of the device, and assist with the analysis of the functional MRI data.

Rationale for Using TRPMS in Stroke Recovery and Preliminary Results

The new device invented by Drs. [name] and [name] is substantially different from conventional TMS devices used in previously published studies. An important difference of this stimulator is that it produces a maximum stimulus strength that is only 6% of the maximum stimulus strength of conventional TMS. Another important difference is that it is much more focal with a spatial spread of about 2 - 3 cm for the stimulus. The frequencies of stimulation used with this device are also lower than those used in conventional stimulation studies. The rationale for using these lower stimulus frequencies is two-fold: 1) We would like to explore whether these reduced stimulus parameters are sufficient to produce the desired effect on recovery from stroke; and 2) This device uses a different mechanism for delivery of each stimulus, namely an oscillatory pulse of 100 ms duration. We believe that this is a more physiological and effective stimulus to bring about restorative neuroplastic changes in stroke, and does not require the higher frequencies of stimulation used in conventional TMS therapy.

Patients

Patients with chronic ischemic stroke with measurable unilateral motor deficit of arm and leg (or arm alone) of more than 3 months duration will be included in the study. Informed consent will be obtained from the patients.

The inclusion criteria for the study are:

- 1) Patients aged 18 to 80
- 2) Clinical diagnosis of chronic ischemic stroke recovering for more than 3 months with unilateral motor deficits of arm and leg, or arm alone

The exclusion criteria are:

- 1) History of seizure
- 2) Epileptogenic activity (indicative of increased risk of seizures) on EEG
- 3) Any active unstable medical condition
- 4) Pregnancy
- 5) Schizophrenia, bipolar disorder, alcoholism, or substance abuse
- 6) Medications which in the investigator's clinical judgment significantly lower the seizure threshold

- 7) Presence of metal or electronic implants in the head (or any in the body that preclude MRI), including pacemakers, defibrillators, aneurysm clips, neuro-stimulators, cochlear implants, metal in the eyes, etc.
- 8) Any changes in medications prescribed for the treatment of stroke impairment within six weeks prior to inclusion in the study or at any time during the study
- 9) Botulinum toxin use within 2 months prior to the Screening Visit or any planned use of botulinum toxin during the study
- 10) Changes in NIHSS and motor assessment scores between Visit 1 and Visit 2 indicating that the patient's impairment is not stable. The following cutoffs, based on research establishing Minimal Clinically Important Differences, will be used for this determination:
 - National Institutes of Health Stroke Scale: A change in total score of more than 2 points in either direction, or a change in the motor extremity score of more than 1 point in either direction.
 - Fugl-Meyer Assessment of Sensorimotor Impairment: A change of more than 5 points in either direction on the upper-extremity motor score for the affected arm.
 - Action Research Arm Test: A change of more than 5 points in either direction on the ARAT score for the affected arm.
- 11) Any condition that precludes a high quality brain MRI scan.

Study Questionnaire

Each subject will be asked to fill out a questionnaire on an electronic tablet before and after each study session, as we have done in prior studies, in order to assess any subjective effects and adverse reactions to the mild magnetic stimuli delivered during the session.

Evaluation of Patients

Clinical evaluation of patients before (at two time points more than one week apart) and immediately after treatment and at one week, one month and three month follow-up time points will include National Institutes of Health Stroke Scale (NIHSS), grip strength (with hand dynamometer), pinch strength (with pinchmeter), gait speed (Timed Up and Go test), Fugl-Meyer motor arm assessment and Action Research Arm Test (ARAT). All motor function tests will be done by an external physical therapist under the guidance of the PI.

Primary endpoint:

Post-treatment increase in the number of activated voxels in the cortical areas surrounding the lesion, namely precentral gyrus, premotor cortex, supplementary motor cortex, paracentral lobule, and postcentral gyrus, in functional MRI scans conducted at baseline (Visit 2) and immediately post-treatment (Visit 23). The brain voxels are activated by grasping movements performed or attempted by the patient with the affected hand in the MRI machine during acquisition of the functional MRI scan.

Secondary endpoints will be:

- 1) Change in the Fugl-Meyer motor arm score between baseline (Visit 2) and immediately post-treatment (Visit 23).
- 2) Change in National Institutes of Health Stroke Scale (NIHSS) score between baseline (Visit 2) and immediately post-treatment (Visit 23).
- 3) Change in the ARAT score between baseline (Visit 2) and immediately post-treatment (Visit 23).
- 4) Change in grip strength score between baseline (Visit 2) and immediately post-treatment (Visit 23).
- 5) Change in pinch strength score between baseline (Visit 2) and immediately post-treatment (Visit 23).
- 6) Change in Timed Up and Go test score between baseline (Visit 2) and immediately post-treatment (Visit 23).

Schedule of Assessments							
	Visit 1	Visit 2	Visit 3-22	Visit 23	Visit 24	Visit 25	Visit 26
	Pre-treatment	Pre-treatment 1 week later	Treatments	Immediately Post-treatment	1 week Post treatment	1 month Post treatment	3 months Post treatment
NIHSS	X	X		X	X	X	X
Grip strength	X	X		X	X	X	X
Pinch strength	X	X		X	X	X	X
Timed Up and Go (gait speed)	X	X		X	X	X	X
Fugl-Meyer assessment	X	X		X	X	X	X
ARRT (Action Research Arm Test)	X	X		X	X	X	X
Electroencephalography (EEG)	(X) ¹	(X) ¹					
fMRI	(X) ¹	(X) ¹		X		X	
Electromyography (EMG)	(X) ¹	(X) ¹		X		X	
TRPMS Treatment			X				
1= can be performed at either visit							

Multifocal Transcranial Rotating Permanent Magnet Stimulation (TRPMS) Treatment

TRPMS microstimulators will be attached to a specially chosen tight fitting neoprene cap by Velcro at stimulus sites determined as described below. The patient will be assisted in wearing the flexible cap on his/her head. The cap is essentially similar to a diving or swimming cap, and fits and feels exactly the same when worn. Two microstimulators will be attached to the primary motor cortical (PMC) sites (one medial and one lateral spaced at a distance of 4 cm) on the contralesional side. On the ipsilesional side one microstimulator each will be attached to the lateral premotor cortical (LPC) and supplementary motor cortical (SMC) sites. In addition, on the ipsilesional side two microstimulators will be placed on sites surrounding the lesion on the PMC or the postcentral gyrus spaced 4 cm apart. The stimulus protocol will be preprogrammed and uploaded to a Bluetooth-enabled microcontroller driving the device, to be turned on using a smartphone app. The researcher administering the treatment will turn the stimulator on. The stimulator turns off by itself at the end of the treatment on any given day. But if it needs to be turned off before that then the researcher can easily do so. Treatment will be of four weeks' duration. It will consist of 40 min repeated TRPMS stimulation Monday through Friday. For low frequency stimulation on the contralesional side (PMC) the stimulus pulse duration will be 100 ms and frequency will be 0.2 Hz. The effectiveness of these parameters in modulating cortical neuronal activity has been established by our prior studies[13, 14]. For ipsilesional side (PMC, LPC and SMC) the stimulus duration and frequency will be 25 ms and 5 Hz, respectively.

EEG Recording

EEG recording of 30 min duration will be conducted before the four week treatment using the 10-20 international system EEG. EEG data will be examined visually for the presence of epileptiform activity or other abnormalities. Power spectral analysis of the entire EEG data will be conducted using EEG lab toolbox (Swartz Center for Computation Neuroscience, Institute for Neural Computation, the University of California San Diego, San Diego, CA) to detect the presence of abnormal spectral peaks and changes. This procedure will be done for safety monitoring and will not be included in the statistical analysis.

Anatomical and Functional MRI

Anatomical MRI scan (T1-weighted 3D-MPRAGE) and fMRI (single shot echoplanar imaging³; TR = 2000 ms, TE = 30 ms, 36 slices, slice thickness 4 mm, no gap, matrix 64x64, FOV 22 cm) will be carried out on a 3.0 T Philips Ingenia MRI scanner at the HMRI imaging core facility. After the standard anatomical MRI scan a 7.5 minute event-related and a 5 min resting state fMRI scans will be conducted on all patients. The task performed by the patients in the scanner for the event-related scan will be 30 second attempted or actual gripping movements with the affected, unaffected and both hands, sequentially, alternating with 30 second rest periods in a simple block design. The movements and rest periods will be triggered by instructions on the overhead display in the scanner. This will allow us to determine the blood oxygenation level-dependent (BOLD) response in the contralateral PMC on both sides in real time. Each patient will be asked to wear our nylon magnetic stimulation device cap on which EEG 10-20 C3 and C4 fiducial loci will be marked by attached vitamin E capsules that show up on MRI scans. These markings will allow us to pinpoint the sites of stimulation for the subsequent magnetic stimulation treatment. During resting state fMRI the patient will be asked to look at a blank screen displaying a fixation cross. fMRI data will be resampled into 4 mm x 4 mm x 4 mm voxels and preprocessed with SPM12 (Wellcome Department of Cognitive Neurology, London,

UK) using the method of Ashburner and Friston[15]. The analysis of fMRI data will consist of general linear model-based estimation of the event-related BOLD response in each patient using SPM12 software program, as well as fcMRI computation.

Functional Connectivity Analysis

Using in-house MATLAB scripts and functions we will compute the strengths of connections in the fMRI time series data between stimulated volumes (half spheres of 2.4 cm diameter localized in MNI space with MRICRON (Chris Rorden, 2013) and converted to matrix coordinates using mni2cor function (Xu Cui, 2012)) by measuring the partial correlation coefficient (ρ) between pairs of voxel time series. The ρ coefficients will be transformed to z scores, and the high threshold set at $z = 2.5$. ROI coordinates will be obtained from the automated anatomical labeling template[16].

Granger Causality Analysis

In addition to the functional connectivity between cortical regions and their targets we will estimate effective (or directed) connectivity between these regions with the concept of Granger causality [17, 18]. Granger causality will be computed between the average signal in the stimulated region and voxel-wise in the target region, in order to create a causality map for each patient. Statistical significance thresholds will be computed by adaptation of an established test[19] based on random trial perturbations. The maps will be multiple test corrected using a procedure that has been applied to Granger causality testing before[20].

Electromyography

To detect and assess muscle activity during attempted gripping or push down movements with the affected hand and compare it with the normal hand we will perform non-invasive electromyography (EMG) of two intrinsic muscles of each hand, namely abductor pollicis brevis (APB) and first dorsal interosseous (FDI) muscles. Subjects will be required to follow alternately flashed instructions on a computer screen to perform gripping and push down movements with each of their hands at their own pace in a serial block design. Movements of 14 s duration will be alternated with 14 s pauses. The total duration of recording will be ~7.5 min. It will be done on the day of the fMRI scan up to one week before, one day after and one month after the treatment.

We will use self-adhesive surface electrodes (Covidien Kendall 130 foam electrodes, Covidien LLC, Mansfield, MA) attached to the thenar eminence for APB and the dorsal part of the web between the thumb and the index finger for FDI. We will conduct bipolar recordings referenced to the base of the index finger with a ground strap or self-adhesive electrode attached to the wrist. Recordings will be carried out using a wireless EMG system (BioRadio, Great Lakes NeuroTechnologies, Valley View, OH) with a sampling rate of 4 kHz. For counting the number of motor potentials, we will filter the EMG traces using a 20 – 500 Hz digital band pass filter (idealfilter function in MATLAB, Mathworks, Inc., Natick, MA). In our in-house MATLAB graphical user interface program we will then set a cutoff threshold at a level corresponding to positive and negative amplitudes of 15 μ V from upper and lower limits of baseline set manually by visually examining each recorded trace one by one. The MATLAB program counts the biphasic or polyphasic peaks that overshoot this threshold. In the computer program peak-to-peak amplitudes are calculated by adding the largest positive and negative peak amplitudes of the

biphasic/polyphasic transients. The peak-to-peak durations correspond to the interval between the peak time points of these largest amplitudes.

Statistical Analysis of Data

For this initial phase clinical trial, sample size power calculation was not performed; rather, a sample size of 30 comparable to that used in prior rTMS stroke Phase 1 trials was chosen. Non-parametric methods of statistical analysis were employed because of the sample size and non-Gaussian distribution of data. The Mann-Whitney U test was applied for comparison of rank ordered values and pre-/post-treatment differences between active and sham treatment arms. Within-subject comparison across time points was done using the Wilcoxon signed rank test. Pair-wise comparison of proportions of subjects between groups involved application of Fisher's exact test. Finally, linear regression models were used to test for significant interactions between treatment effects and age, time in months since the stroke, and cortical versus subcortical infarct location. Level of significance was set at 5%.

Anticipated Results

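### Criterion 10 cannot show that recovery has ended, and the active-v-sham comparison is neither stratified nor adjusted for time since stroke

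*Combined protocol and SAP*

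**What the plan says.** **Eligibility.** Inclusion criterion 2 (Patients) asks for "Clinical diagnosis of chronic ischemic stroke recovering for more than 3 months with unilateral motor deficits of arm and leg, or arm alone". No maximum time since stroke is set.

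**Stability screen.** Exclusion criterion 10 compares Visit 1 with Visit 2, and failing any one cutoff excludes the patient. The cutoffs, which the plan says derive from minimal clinically important differences, are:
- NIHSS (points): "A change in total score of more than 2 points in either direction, or a change in the motor extremity score of more than 1"
- Fugl-Meyer: "A change of more than 5 points in either direction on the upper-extremity motor score for the affected arm"
- ARAT: "A change of more than 5 points in either direction on the ARAT score for the affected arm"

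**Interval.** The Schedule of Assessments labels Visit 2 "Pre-treatment 1 week later". Evaluation of Patients instead puts the two pre-treatment assessments more than one week apart and gives no maximum.

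**Outcome window.** Primary and secondary endpoints are changes from Visit 2 to Visit 23, which spans four weeks of treatment.

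**Allocation.** The opening paragraph gives 1:1 allocation, 15 per arm, from a "list of random numbers generated by a hardware real random number generator for randomization". It mentions no stratification.

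**Analysis.** Statistical Analysis of Data compares the arms by Mann-Whitney U and time points within subjects by Wilcoxon signed rank. It adds that "linear regression models were used to test for significant interactions between treatment effects and age, time in months since the stroke" and infarct location. It does not say which outcomes are modelled, or whether an adjusted treatment effect will be reported.

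**The concern.** The trial is described as one in chronic stroke, and criterion 10 is there to remove patients whose impairment is still changing. It applies a cutoff the size of a clinically important change to roughly a quarter of the outcome window. A patient improving slowly but steadily passes the screen and can then accumulate a change of that size by Visit 23 without any treatment effect.

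Because entry opens just after 3 months and never closes, such patients can be mixed with patients who reached a plateau long ago. Their natural gain adds spread to the change scores in a trial with 15 per arm, and an uneven split between arms shifts the estimated difference. Time since stroke is the obvious baseline marker for this. The plan already uses it, but to look for effect modification, not to sharpen the arm comparison.

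The within-subject Wilcoxon tests are more exposed, because they have no concurrent control.

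**Working it through.** The plan states that no power calculation was done, so there is no figure of its own to reproduce. Inputs from the documents are the cutoffs, the run-in interval, the four-week treatment period, 15 per arm and the 5% level (taken as two-sided). The number still recovering, their extra gain (drift), the SDs and the effect size are assumptions.

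**1. What the Fugl-Meyer screen lets through.** Suppose a patient gains r points a week, the run-in is one week, and the visit-to-visit difference has SD s. Scores are whole numbers, so

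P(excluded) = 1 − [Φ((5.5 − r)/s) − Φ((−5.5 − r)/s)].

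For r = 1 to 2, which is 4 to 8 points over four weeks, and s = 1 to 3, this runs from about 0% (r = 1, s = 1) to 12.8% (r = 2, s = 3). The ARAT cutoff has the same 5-point tolerance. The NIHSS cutoffs allow changes of up to 2 points in total and 1 in the motor extremity score.

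**2. Chance imbalance at 15:15.** With K of 30 patients still recovering, the number in one arm is hypergeometric. For K = 10:
- P(5 v 5) = C(10,5)·C(20,10)/C(30,15) = 252 × 184,756 / 155,117,520 = 0.300
- P(6 v 4, either way) = 2 × 210 × 167,960 / 155,117,520 = 0.455
- P(arms differ by 4 or more) = 1 − 0.300 − 0.455 = 0.245

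For K = 8 and K = 12 the figures are 0.215 and 0.264. For K = 10, a difference of 6 or more has probability 0.050.

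**3. Shift from a 7 v 3 split.** (7 − 3)/15 × drift = 0.267 × 4 = 1.1 points, or 0.267 × 8 = 2.1 points.

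**4. Type I error of the Mann-Whitney test** (simulation, 40,000 trials per row, K = 10, SD 4):

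| Drift | Over all allocations | Given 7 v 3 | Given 8 v 2 |
|---|---|---|---|
| 2 | 0.044 | 0.055 | 0.067 |
| 4 | 0.045 | 0.066 | 0.142 |
| 8 | 0.046 | 0.093 | 0.303 |

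**5. Within-arm Wilcoxon with no treatment effect** (5 of 15 recovering, SD 4): it rejects in about 9%, 17% and 32% of trials for drift 2, 4 and 8.

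**6. Power for a 4-point effect** (K = 10, SD 4), unadjusted Mann-Whitney against a rank test stratified by recovery status:

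| Drift | Recovery status known exactly | Proxy 80% accurate |
|---|---|---|
| 4 | 0.60 to 0.69 | 0.62 to 0.63 |
| 8 | 0.45 to 0.71 | 0.43 to 0.53 |

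With no drift, the stratified test loses about 0.03. Over residual SDs of 4 to 6 and allowing for simulation error, the gain is about 0.01 to 0.10 for drift 4 and about 0.03 to 0.27 for drift 8.

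**The case against.** The best defence is the concurrent randomised sham arm. Natural recovery is balanced in expectation, and the type I error over all allocations stays below 5%. That stands. A reader might infer that recovering patients bias the arm comparison; the design does not support this. The raised error rates after a 7 v 3 or 8 v 2 split are offset by lower rates when the split is even. The same argument could be made for any prognostic factor left unstratified in a pilot of 30.

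Three other stronger readings are tempting and should be resisted:

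- **That nothing in the plan takes account of time since stroke.** It enters linear regression models with treatment. What is missing is stratification and a stated adjusted arm comparison. Whether those models carry main effects is not said.
- **That the screen admits 20 points of recovery.** 5 points a week × 4 weeks = 20 is a linear extrapolation at the exact limit. With a two-week gap, which the text permits, it is 5/2 × 4 = 10. The NIHSS and ARAT cutoffs can also exclude.
- **That adjustment lifts power to about 75%.** A linear model gives 0.74 (drift 4) and 0.73 (drift 8), against 0.62 and 0.42 unadjusted, but only if it knows exactly who is still recovering, the data are Gaussian and the SD is 4. Time since stroke is only a proxy, and the plan chose non-parametric methods because it regards the data as non-Gaussian. At SD 6 with drift 4, even exact knowledge moves power only from 0.38 to 0.42.

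Finally, all these figures concern Fugl-Meyer, a secondary endpoint. The primary endpoint is the activated-voxel count. The schedule shows one pre-treatment scan, at either visit, so voxel count has no stability check, but nothing in the documents shows how far it drifts with recovery.

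**Conclusion.** The point holds as a matter of precision and interpretation, not of bias between arms. Criterion 10 screens out gross fluctuation over about a week; it does not establish that recovery has ended. With no stratification described and an unadjusted arm comparison, a baseline value the plan already uses is left out where it could help most.

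The size rests on assumptions. If 8 to 12 of 30 patients are still recovering, the chance that the arms differ by 4 or more of them is 21.5% to 26.4%. The benefit of adjusting is nil or slightly negative if there is no drift, small to moderate at 4 points, and potentially large at 8 points only if time since stroke identifies the recovering patients well. The within-arm tests are the part that randomisation does not protect.

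**What to change.** Leave eligibility as it is.

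1. **Adjusted arm comparison.** Prespecify the active-v-sham comparison of Visit 2 to Visit 23 changes with adjustment for time since stroke, by a method in keeping with the plan's non-parametric choice. Either a rank-based ANCOVA with log time since stroke (recovery flattens with time and the range is open-ended) or a rank test stratified by time since stroke would serve.
2. **Within-arm tests.** State that within-arm Wilcoxon changes are descriptive and will not be read as treatment effects.
3. **Wording.** State that criterion 10 screens for gross fluctuation and does not show a plateau. Reconcile the run-in interval between Evaluation of Patients and the Schedule of Assessments.
4. **Optional.** Have the research associate use two blocked lists stratified by time since stroke. This adds little once the analysis is adjusted: in the linear-model simulation with exact knowledge of recovery status, power was 0.749 with adjustment alone and 0.753 with stratification as well (drift 4), and 0.716 and 0.748 (drift 8).

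The cost is one degree of freedom, a possible power loss of about 0.03 if there is no drift, and slightly more list administration if item 4 is adopted. No new data are needed.

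### Does taking Visit 2 alone as baseline for the six secondary change scores, when Visit 1 readings also exist, waste precision the trial needs?

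*Combined protocol and SAP*

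**What the plan says.** In the combined protocol and SAP, Evaluation of Patients, all six secondary endpoints have the same form. Two examples are "Change in the Fugl-Meyer motor arm score between baseline (Visit 2) and immediately post-treatment (Visit 23") and "Change in grip strength score between baseline (Visit 2) and immediately post-treatment (Visit 23"). NIHSS, ARAT, pinch strength and Timed Up and Go follow the same pattern.

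The Schedule of Assessments marks all six measures at both Visit 1 and Visit 2. The only stated use of the Visit 1 scores is exclusion criterion 10, which removes patients for "Changes in NIHSS and motor assessment scores between Visit 1 and Visit 2 indicating" an unstable impairment. Its cut-offs are:
- NIHSS: more than 2 points on the total, "or a change in the motor extremity score of more than 1 point in either direction"
- Fugl-Meyer arm score: more than 5 points
- ARAT: more than 5 points

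Grip, pinch and Timed Up and Go have no cut-off.

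Statistical Analysis of Data gives the tests: "The Mann-Whitney U test was applied for comparison of rank ordered values and pre-/post-treatment differences between active and sham treatment arms", and "Within-subject comparison across time points was done using the Wilcoxon signed rank test". It mentions no averaging of baselines. It also states that no power calculation was done, and it gives no SD or effect size.

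**The concern.** A change score carries the measurement error of both its readings. With 15 patients per arm, noise in a single baseline reading costs power. A second pre-treatment reading exists for every patient and every secondary endpoint, yet it is used only to screen, and for three of the six measures it has no stated use at all. Averaging would need no new data. If the readings differ only by random error, the plan appears to discard free precision on the endpoints that carry the clinical efficacy question.

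Only secondary endpoints are at stake. The pre-treatment fMRI is done once, at either visit, so the primary endpoint has no second baseline to average.

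**Working it through.** There is no figure in the plan to reproduce. Every SD and correlation below is an assumption.

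**Model.** Let e be the measurement-error SD of one reading, r the SD of true response between patients, and d the SD of true change from Visit 1 to Visit 2. The variance of the change to Visit 23 is:
- Visit 2 alone: 2e² + r²
- Mean of Visits 1 and 2: 1.5e² + r² + d²/4

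Averaging saves 0.5e² − d²/4. The saving is halved at d = e (0.5e² − 0.25e² = 0.25e²), zero at d = √2·e = 1.41e, and negative beyond that.

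**Grip, pinch and Timed Up and Go (no cut-off), d = 0.** The relative saving is 0.5/(2 + r²/e²). Power is for the planned Mann-Whitney test, 15 per arm, two-sided 5%, normal errors, 20,000 simulated trials, with the shift in SDs of the Visit 2 change score.

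| r²/e² | Variance saved | Power at 0.8 SD | Power at 0.5 SD |
|---|---|---|---|
| 0 | 0.5/2 = 25% | 52% to 65% | 24% to 31% |
| 1 | 0.5/3 = 17% | 52% to 60% | 24% to 28% |
| 2 | 0.5/4 = 12.5% | 51% to 58% | 24% to 27% |
| 4 | 0.5/6 = 8% | 53% to 56% | 24% to 26% |

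The first row requires every patient to respond identically. Null rejection was 4.4% to 4.6% with either baseline.

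**The same measures with true change between visits, d = 2e.** At r²/e² = 0, variance rises from 2e² to 2.5e² (+25%). At r²/e² = 1 it rises from 3e² to 3.5e² (+17%), and power at 0.8 SD falls from 51% to 46%. At r²/e² = 4 it rises from 6e² to 6.5e² (+8%), and power falls from 52% to 49%.

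A second parametrisation points the same way. Suppose correlation decays by a factor 0.95 per week, with readings one week apart before treatment and four weeks from Visit 2 to Visit 23. In units of the between-patient variance:
- Visit 2 alone: 2(1 − 0.95⁴) = 0.371
- Mean: 1 + (1 + 0.95)/2 − (0.95⁴ + 0.95⁵) = 0.387
- Ratio: 1.04, so an effect detectable with 80% power under Visit 2 has 78% under the mean.

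**Fugl-Meyer and ARAT.** Criterion 10 already limits the Visit 1 to Visit 2 difference, which leaves less error to average out. Keeping only differences of 5 points or less, with e = 2, 3 and 4:
- r = 3: variance saved 8.4%, 7.1% and 5.4%, about 2 to 3 power points at 0.8 SD
- r = 6: variance saved 3.2%, 3.4% and 3.0%, about 1 power point

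**NIHSS.** With both cut-offs modelled and e from 1 to 2, the saving is 4% to 11% when r = e (1 to 4 power points at 0.8 SD) and 2% to 5% when r = 2e (1 to 2 points).

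**Spill-over of the screen.** Criterion 10 excludes the whole patient. If session-level error is shared across motor tests, it narrows grip, pinch and Timed Up and Go differences too. With Fugl-Meyer and ARAT error SD 3 and between-test error correlation 0.5, the 25%, 17% and 8% savings (r²/e² = 0, 1, 4) become about 20%, 13% and 6.5%. At correlation 0.7 they become about 16%, 11% and 5%.

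**Within-arm tests.** Half of any practice gain between Visits 1 and 2 would enter a change measured from the mean. For a sham arm of 15 with e = r = 3, no true effect and a practice gain of 1, 2 or 3 units, the Wilcoxon test rejects in 6%, 11% and 19% of trials with the mean baseline, against 4% to 5% with Visit 2.

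**The case for a change.** The best argument for averaging is that it costs nothing in data, a practice gain common to both randomised arms cancels between them, and the most favourable case is worth 15/0.75 = 20 patients per arm instead of 15. If averaging were confined to the between-arm Visit 23 test and fixed before unblinding, with Visit 2 alone as a sensitivity analysis, the within-arm problem would not arise. The algebra is right, and under stable status the direction of the gain is certain.

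What stands is that some precision may be left unused. What does not stand is that this makes the plan deficient:
- The gain is largest for grip, pinch and Timed Up and Go, the measures with no stability cut-off of their own, so even its sign is unknown there. The documents give no test-retest data. Evaluation of Patients sets no upper limit on the interval ("Clinical evaluation of patients before (at two time points more than one week apart) and immediately after treatment"), while the schedule has "Pre-treatment 1 week later".
- Where stability is screened, the expected gain is only about 1 to 4 power points at 0.8 SD.
- Confining averaging to one test splits the baseline. Arm-level changes from the Wilcoxon analyses would no longer subtract exactly to the between-arm contrast. The follow-up contrasts at Visits 24 to 26 and the regression models would each need their own decision.
- Statistical Analysis of Data is written in the past tense. If the data are already unblinded, changing the baseline would be a post hoc choice.

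**Conclusion.** The concern does not hold. Visit 2 is a valid, unbiased and consistently stated baseline, the last clinical reading before treatment, and Visit 1 has a purpose of its own as the stability screen. No stated figure is missed, because this pilot sets no power target. Type I error and the primary fMRI endpoint are unaffected.

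On power at a 0.8 SD difference, the cases examined run from a gain of about 12 points (52.3% to 64.7%, with identical response in every patient and no true change between visits) to a loss of about 5 points (51% to 46%, with true between-visit change at twice the error SD and r = e). These figures assume normal errors, whereas the plan describes its data as non-Gaussian, so they show direction and rough size only. Nothing in the documents fixes where in that range the trial lies. Reasonable statisticians could choose either baseline, and the plan's choice needs no change.
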